**Table 3 Classification of Hypoglycemia**

| Hypoglycemia Level | Glycemic Criteria             | Description  |
|--------------------|-------------------------------|--|
| Level 1            | ≤70 mg/dL (3.9 mmol/L)        | Sufficiently low for treatment with fast-acting carbohydrate and dose adjustment of glucose-lowering therapy |
| Level 2            | <54 mg/dL (3.0 mmol/L)        | Sufficiently low to indicate serious, clinically important hypoglycemia                                      |
| Level 3            | No specific glucose threshold | Hypoglycemia associated with severe cognitive impairment requiring external assistance for recovery          |

[AmDA 4 2018](#)

Subjects should be asked about symptomatic and asymptomatic hypoglycemia at each visit, and trained on treatment of hypoglycemia.

### **8.3.4 Nausea, Vomiting and Diarrhea**

Nausea, vomiting, and diarrhea events will be collected. For each event, assessment of severity, duration and relatedness to study drug will be recorded.

### **8.3.5 Acute Pancreatitis**

Acute pancreatitis (AP) is an acute inflammatory process of the pancreas that may also involve peripancreatic tissues and/or remote organ systems. The diagnosis of AP requires two of the following three features:

- Abdominal pain, characteristic of acute pancreatitis (generally located in the epigastrium and radiates to the back in approximately half of the cases; the pain is often associated with nausea and vomiting)
- Serum amylase and/or lipase  $\geq 3$  x ULN
- Characteristic findings of AP on computed tomography (CT) scan or magnetic resonance imaging (MRI)

If a subject experiences severe or serious abdominal pain or if acute/chronic pancreatitis is suspected, administration of study drug should be temporarily discontinued. If AP is suspected, appropriate laboratory tests (including levels of amylase and lipase) should be obtained. These laboratory tests may be obtained locally but, if possible, a serum lipase and amylase should also be sent to the central laboratory (for capture of data in the clinical trial database) at the time of presentation. If serum amylase and/or lipase values are confirmed  $\geq 3$  x ULN, imaging studies, such as abdominal CT scan with or without contrast, MRI, or abdominal ultrasound, to include pancreas and gallbladder, should be performed. If diagnostic testing does not support the diagnosis of acute or chronic pancreatitis then study drug may be resumed as soon as it is safe to do so in the judgment of the investigator. If diagnostic testing supports the diagnosis of acute or chronic pancreatitis or pancreatic cancer,

the subject must permanently discontinue study drug. A review of the subject's concomitant medications should be conducted to assess any potential causal relationship with pancreatitis.

### **8.3.6 Cardiovascular Events**

Deaths (CV and non-CV), nonfatal myocardial infarctions (MIs), and nonfatal strokes that occur during the treatment phase or follow-up phase will be reviewed by the sponsor-designated medical monitor. Investigative sites will also be asked to report any cases of transient ischemic attack (TIA) or hospitalization for unstable angina to the sponsor-designated medical monitor, to ensure that all true stroke and MI events are captured. CV event definitions will be based on the Standardized Definitions for Cardiovascular and Stroke Endpoint Events in Clinical Trials and the ESC/ACCF/AHA/WHF Expert Consensus Document Third Universal Definition of Myocardial Infarction.

### **8.3.7 Electrocardiography (ECG) Findings**

Any treatment emergent clinically significant ECG finding should be reported as an AE in the eCRF.

If a clinically significant increase in the QT/corrected QT (QTc) interval from baseline or other clinically significant quantitative or qualitative change from baseline is identified, the subject will be assessed by the investigator for symptoms (for example, palpitations, near syncope, syncope) and to determine whether the subject can continue in the trial. The investigator or qualified designee is responsible for determining if any change in subject management is needed and must document his/her review of the ECG printed at the time of evaluation from at least one of the replicate ECGs from each time point.

## **8.4 Liver Function Monitoring**

If a study subject experiences elevated ALT or AST  $>3$  x ULN or elevated total bilirubin  $>2$  x ULN, clinical and laboratory monitoring should be initiated by the investigator ([Appendix 3](#)). Details for hepatic monitoring depend upon the severity and persistence of observed laboratory test abnormalities. To ensure subject safety and comply with regulatory guidance, the investigator will consult with the sponsor-designated medical monitor regarding collection of specific recommended clinical information and follow-up laboratory tests.

## **8.5 Serum Creatine Kinase Monitoring**

If a study subject experiences CK  $>5$  x ULN that suggests muscle damage, the subject should be evaluated for any muscle-associated symptoms as well as any clinical signs of myalgia,

---

generalized weakness, or darkened urine. Additional clinical and laboratory monitoring should be initiated by the investigator, in consultation with the sponsor-designated medical monitor. Laboratory monitoring should include repeat CK testing as well as assessment of coagulation factors (prothrombin time, activated partial thromboplastin time, INR), urine myoglobin, cardiac troponin I, and additional testing as clinically indicated.

## 8.6 Serum Calcitonin Monitoring

Serum calcitonin  $\geq 20$  pg/mL at screening is exclusionary (see section 4.2). The subject will be referred to a thyroid specialist for further evaluation and will be discontinued from screening.

Any treatment-emergent serum calcitonin value  $\geq 20$  pg/mL will be reviewed by the DSMB along with relevant supplementary data (eg, demographics and medical history, concomitant medications, supplemental laboratory tests and relevant AE data). The DSMB will provide recommendations to the investigator for individual subjects, including diagnostic procedures, treatment, and continuation of the study drug according to a pre-specified algorithm:

- Calcitonin  $>ULN$  and  $<20$  pg/mL

The investigator shall evaluate factors potentially leading to calcitonin elevation. Calcitonin sampling shall be performed at intervals indicated in the protocol with no further action unless levels rise to  $\geq 20$  pg/mL. If the value is the final one in the trial, the subject shall be referred to a thyroid specialist for further evaluation.

- Calcitonin  $\geq 20$  pg/mL and  $\leq 50$  pg/mL

Calcitonin sampling shall be performed at intervals indicated in the protocol with no further action unless levels rise to  $\geq 50$  pg/mL. No impact on continuation of trial treatment. If the value is the final one in the trial, the subject shall be referred to a thyroid specialist for further evaluation.

- Calcitonin  $\geq 50$  pg/mL

If calcitonin is confirmed to be  $\geq 50$  pg/mL, then the DSMB shall recommend the study investigator remove the subject from study treatment. The subject shall be referred to a thyroid specialist for further evaluation.

## 8.7 Treatment Discontinuations

If a subject's treatment is discontinued as a result of an AE, study site personnel must clearly report (via eCRF) the circumstances and data leading to discontinuation of treatment.

## 8.8 Pregnancies

Cases of pregnancy that occur during maternal or paternal exposures to study drug should be reported. Data on fetal outcome and breast-feeding will be collected for regulatory reporting and drug safety evaluation. Pregnancies and female partner pregnancies will be followed until 6 weeks following delivery to determine the outcome.

## 8.9 Serious Adverse Events (SAEs)

The collection of SAEs begins after the subject has signed the ICF. SAEs occurring after the subject has received study drug are treatment-emergent SAEs (TESAEs).

An SAE is defined by the investigator or sponsor as any AE resulting in any of the following outcomes:

- death
- life-threatening AE
- in-patient hospitalization or prolongation of existing hospitalization
- a persistent or significant disability/a persistent or significant incapacity or substantial disruption of the ability to conduct normal life functions

Important medical events that may not result in death, be life threatening, or require hospitalization may be considered an SAE when, based upon appropriate medical judgment, they may jeopardize the subject and may require medical or surgical intervention to prevent one of the outcomes listed in this definition. Examples of such medical events include allergic bronchospasm requiring intensive treatment in an emergency room or at home, blood dyscrasias or convulsions that do not result in inpatient hospitalization, or the development of drug dependency or drug abuse.

Planned surgeries should not be reported as SAEs unless the underlying medical condition has worsened during the course of the trial.

Suspected unexpected serious adverse reactions (SUSARs) are serious events that are not listed in the IB or are not listed at the specificity or severity that has been observed.

### 8.9.1 Reporting Serious Adverse Events

#### 8.9.1.1 Initial Report

All SAEs occurring from the time of informed consent until 30 days following the last administration of study drug must be reported to Medpace Clinical Safety **within 24 hours** of the knowledge of the occurrence (this refers to any AE that meets any of the aforementioned serious criteria). All known SAEs that the investigator considers related to study drug *occurring after the 30-day follow-up period* must be reported to the sponsor.

---

*Confidential*

To report the SAE, complete the SAE form electronically in the EDC system for the study. When the form is completed, Medpace Safety personnel will be notified electronically and will retrieve the form.

If the event meets serious criteria and it is not possible to access the EDC system, send an email to Medpace Safety (email address listed below) or call the Medpace SAE hotline (phone number listed below), and fax the completed paper SAE form to Medpace (fax number listed below) within 24 hours of awareness. When the EDC system becomes available, the SAE information must be entered within 24 hours of the system becoming available.

#### **8.9.1.2 Follow-up Reports**

Within 24 hours of receipt of follow-up information, the investigator must update the SAE form electronically within the EDC system and submit any supporting documentation (eg, subject discharge summary or autopsy report) to Medpace Clinical Safety using the contacts listed above for initial reporting.

### **8.10 Safety Monitoring**

#### **8.10.1 Safety Monitoring**

A study level safety review will be conducted to monitor and assess safety data collected during the study. Specifically, any signs or trends indicating potential underlying safety issues will be identified. The safety review will be scheduled regularly and reviewed by the sponsor-designated medical monitor. More details will be provided in the safety monitoring plan (SMP) including the type of safety data, frequency of review, and unblinding plan if necessary.

The sponsor-designated medical monitor will routinely review:

---

*Confidential*

- trends in safety data laboratory analytes
- serious and non-serious AEs including AESIs (see section 8.2)
- reported pancreatitis and major CV events

### **8.10.2 Assessment of Tolerability**

The safety and tolerability of the 70 mg QW dose level will be assessed by the DSMB following completion of visit 7 (2 weeks of dosing) by at least 10 subjects randomized to OPK-88003. If five or more of those subjects experience severe vomiting or severe nausea defined as an SAE, then the dose of OPK-88003 will be reduced to 60 mg for all subjects including those receiving 70 mg at the time of safety review. Only members of DSMB will gain access to safety data. Members of the DSMB will not have access to efficacy data for this assessment. Study team and site personnel will remain blinded.

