## 5 DISCONTINUATIONS

### 5.1 Discontinuation of Study Drug

#### 5.1.1 *Temporary Discontinuation of Study Drug*

After randomization, the investigator may decide to temporarily discontinue study drug, for example, due to an AE or a clinically significant laboratory value. Every effort should be made by the investigator to maintain subjects in the study and to restart study drug promptly as soon as it is safe to do so. The dates of study drug discontinuation and re-start will be documented. If a subject misses more than four doses of study drug throughout the course of the study or two consecutive doses during the dose escalation phase, they should be discontinued from the study (see section 5.2).

Subject noncompliance with study drug regimen should not be recorded as temporary discontinuation of study drug (see section 7.11).

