#### 5.1.2 *Permanent Discontinuation of Study Drug*

Permanent discontinuation of the study drug during the dose escalation and maintenance phase should be considered by the investigator, after consultation with the sponsor designated medical monitor, when the subject meets the following conditions:

- Abnormal liver tests:
  - Alanine aminotransferase (ALT) or aspartate aminotransferase (AST) >8 x ULN
  - ALT or AST >5 x ULN for more than 2 weeks
  - ALT or AST >3 x ULN and (total bilirubin level >2 x ULN or INR >1.5)
  - ALT or AST >3 x ULN with the appearance of fatigue, nausea, vomiting, right upper-quadrant pain or tenderness, fever, rash, and/or eosinophilia (>5% compared to baseline)
- AEs:
  - Confirmed pancreatitis or pancreatic cancer (see section 8.3.5)
  - Estimated glomerular filtration (eGFR) <30 mL/min/1.73 m^2
  - Any severe injection site reaction or two or more moderate injection site reactions occurring a week or more apart (see section 8.3.1)
  - Any study drug related systemic hypersensitivity reaction (see section 8.3.2)
  - Any nonfatal major CV events (see section 8.3.6)

- Any SAE or clinically significant event (CSE) judged to be related to study drug. A CSE is defined as a moderate to severe AE, abnormal clinical sign, or clinical laboratory finding that may pose a risk to the wellbeing of the subject. A CSE will be determined by the investigator, and may include findings that do not fulfil the criteria for SAEs ([Appendix 2](#)).
- Any other TEAE, SAE or clinical significant laboratory value for which the investigator believes that permanent study drug discontinuation is the appropriate measure to be taken.
- Serum calcitonin with an absolute value of  $\geq 50$  pg/mL on repeat testing
- The subject intentionally or repeatedly takes more than the prescribed dose of study medication.

Subjects who are permanently discontinued from study drug will be discontinued from the study (see section [5.2](#)).

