## 5.2 Discontinuation of Subjects

If the investigator site identifies a subject who did not meet eligibility criteria but was inadvertently randomized, the sponsor-designated medical monitor must be contacted.

If the sponsor or designee identifies a subject who did not meet enrollment criteria and who was inadvertently randomized, the investigator site will be notified. A discussion must occur between the sponsor-designated medical monitor and the investigator to determine whether the subject may continue in the study. Inadvertently randomized subjects may be maintained in the study when the sponsor agrees with the investigator that it is medically appropriate for that subject. The investigator must obtain documented approval from the sponsor to allow the inadvertently enrolled subject to continue in the study.

A subject will be discontinued from the study in the following circumstances:

- The subject requests to be withdrawn from the study.
- The subject is permanently discontinued from study drug (see section [5.1.2](#)).
- The subject misses more than four doses of study drug over the course of the study, or misses two consecutive doses of study drug during the dose escalation phase.
- Enrollment in any other interventional clinical trial.
- The sponsor stops the study or stops the subject's participation in the trial for medical, safety, regulatory or other reasons consistent with applicable laws, regulations and good clinical practice (GCP).

- The investigator decides it is in the best interests of the subject not to continue in the study.
- The subject and/or blinded study staff become unblinded to the subject's treatment assignment.
- Any medication for weight loss is given for more than one week.
- If the subject, for any reason requires treatment for greater than one week with another therapeutic agent that has been approved for treatment of diabetes. A change in dose of metformin is not allowed, unless a temporary increase in dose is needed to treat hyperglycemia (see section 6.11). However, a change to an equivalent dose strength of metformin from immediate-release to extended-release (or vice versa) formulations is allowed.

Subjects discontinued from the study will be requested to complete an early termination (ET) visit as soon as possible (section 9.5). Subjects will be requested to complete a follow-up visit (see section 9.5) four weeks after their final dose.

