## Appendix 2. Clinically Significant Events

Table 5 summarizes the type and severity of symptoms, clinical signs, and clinical laboratory findings that may qualify as a CSE and lead to discontinuation (see section 5.1.2). They are intended as a guideline to the investigator, not as a set of absolute criteria. The underlying principle is to define a level of moderate-to-severe abnormality in safety findings that could cause harm to health, and would preclude further dosing of a subject who experiences this effect. Safety parameters not included in this table may be interpreted in a similar fashion according to investigator judgement.

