**Table 5 Clinically Significant Events**

| Parameter                                     | AE level   |
|---|--|
| Symptoms                        |  |
| Severe Hypoglycemia                           | One episode of severe hypoglycemia defined as low blood glucose with mental status impairment severe enough to require third-party assistance.   |
| Severe Nausea and Vomiting             | Requires IV hydration or emergency department visit or hospitalization, or prevents daily activity.  |
| Dizziness/Hypotension                         | Orthostatic CNS symptoms (dizziness, confusion) that are not vasovagal responses to provocative stimuli (for example, phlebotomy, nausea, bowel or bladder function), and are associated with orthostatic SBP decrease >20 mm Hg or DBP decrease >10 mm Hg or heart rate >105 bpm, confirmed to persist for >3 hours |
| Headache/Pain                                 | Any focal or generalized head pain that disrupts normal activities and is not responsive to medical therapies  |
| Pruritus                                      | Generalised itching over >24 hours unresponsive to oral antihistamine  |
| Signs                           |  |
| Systolic blood pressure                       | >30 mm Hg increase from baseline values and an absolute level >190 mm Hg a  |
| Diastolic blood pressure                      | >20 mm Hg increase from baseline values and an absolute level >115 mm Hg a  |
| Heart rate                                    | Resting (sitting or recumbent) HR >120 bpm   |
| QTc   | >500 msec or >60 msec increase from baseline value a  |
| QRS morphology                                | Significant prolongation of QRS interval or new onset of bundle branch block   |
| Clinical Laboratorya |  |
| Hemoglobin                                    | Absolute value <10 g/dL and >2 g/dL reduction from baseline  |
| Neutropenia                                   | Absolute neutrophils <1,500/ $\mu$ L and >1,000 $\mu$ L decrease from baseline   |
| Lymphopenia                                   | Absolute lymphocyte count <800/ $\mu$ L and >500/ $\mu$ L decrease from baseline   |
| Platelet count                                | <75,000/ $\mu$ L and >50,000/ $\mu$ L decrease from baseline   |
| Creatinine                                    | >2 mg/dL and >0.5 mg/dL increase from baseline value   |

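### Read literally, the Protocol 8.10.2 trigger for cutting 70 mg to 60 mg counts events only in visit 7 completers, so subjects withdrawn for the event before visit 7 are missed (minor)

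*Protocol*

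**What the plan says.** Protocol 8.10.2 has the DSMB assess the 70 mg level "following completion of visit 7 (2 weeks of dosing) by at least 10 subjects randomized to OPK-88003. If five or more of those subjects" meet the event definition, the dose falls to 60 mg for all subjects. The event is in the same sentence: "If five or more of those subjects experience severe vomiting or severe nausea defined as an SAE". Section 3.1 describes the same reduction as something that may happen; 8.10.2 says it will.

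The first 70 mg dose is given at visit 5 (week 8), and visit 7 is at week 10.

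Section 5.1.2 lists grounds on which the investigator, after consulting the medical monitor, should consider stopping study drug permanently. One is "Any SAE or clinically significant event (CSE) judged to be related to study drug". Appendix 2, offered as a guideline, describes clinically significant events as abnormalities that could harm health and "would preclude further dosing of a subject who experiences this effect". Its Table 5 includes severe nausea and vomiting, at the level "Requires IV hydration or emergency department visit or hospitalization, or prevents daily activity".

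Section 5.1.2 then states: "Subjects who are permanently discontinued from study drug will be discontinued from the study". Under 5.2, "Subjects discontinued from the study will be requested to complete an early termination (ET) visit as soon as possible".

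In the other direction, 5.1.1 says of temporary interruption: "Every effort should be made by the investigator to maintain subjects in the study and to restart study drug promptly".

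**The concern.** The event that the rule counts is also a way out of the counted group. The words *those subjects* follow a clause that identifies OPK-88003 subjects by completion of visit 7. A subject who has serious vomiting after the first 70 mg dose, is judged drug-related and is withdrawn goes to an early termination visit and never completes visit 7. No other part of the protocol or SAP adds that subject to the count.

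This is the only pre-specified trigger that lowers the target dose for everyone. As worded, it loses events in the situation it was written for: 70 mg is badly tolerated and affected subjects leave. The decision then rests on DSMB discretion instead of the stated rule.

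**Working it through.** **Stated figure.** The rule is five or more events among at least 10 visit 7 completers. The documents give no trigger probability for it, so there is nothing to reproduce. The operating characteristics below are illustrations.

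**Inputs.** From 8.10.2: 10 completers and a trigger of five. Assumed, because the documents give neither for 70 mg: p, the rate of the counted event after starting 70 mg; and d, the share of affected subjects who leave before visit 7. The review is taken at the tenth completer.

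**Literal reading.** The event rate among completers is q = p(1−d)/(1−pd). The chance of meeting the trigger is P(Bin(10, q) ≥ 5).

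**Leavers counted.** Let L be the number of affected subjects who left among those starting 70 mg before the tenth completer did: L ~ NegBin(10, 1−pd). The chance is P(Bin(10, q) + L ≥ 5). The mean number counted is 10/(1−pd).

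**Worked cases, d = 0.5.**
- p = 0.3: q = 0.15/0.85 = 0.176. Literal 0.020; leavers counted 0.278, with a mean of 10/0.85 = 11.8 subjects counted.
- p = 0.5: q = 0.25/0.75 = 0.333. Literal 0.213; leavers counted 0.796, with a mean of 10/0.75 = 13.3 subjects counted.

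**Chance of meeting the trigger if none / half / all of the affected subjects leave:**

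| Assumed event rate | Literal | Leavers counted |
|---|---|---|
| 10% | 0.16 / 0.01 / 0% | 0.16 / 0.46 / 0.9% |
| 20% | 3.3 / 0.3 / 0% | 3.3 / 7.5 / 13% |
| 30% | 15 / 2 / 0% | 15 / 28 / 42% |
| 50% | 62 / 21 / 0% | 62 / 80 / 91% |

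At a 5% rate, both readings give under 0.05% in every column. The 50% row is the rate that five of 10 implies. With leavers counted, the chance rises above the no-leaver value because five is then applied to more than 10 subjects.

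**Example.** Thirteen subjects start 70 mg and all are due visit 7 by the cut-off. Six have the event, three of those six are withdrawn, and 10 complete visit 7. The literal count is 3 (no cut); the full count is 6 of 13 (cut).

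**Which leavers to add.** A tempting repair is to add anyone who stopped drug by the cut-off. That brings in recent starters who stopped and omits recent starters who are event-free, so it selects events. I simulated staggered entry with 70 active subjects over about 5 months (roughly 22 weeks), about 3.2 per week, and leaving times assumed uniform over the two weeks (40,000 runs). That repair meets the trigger in about 2% (10% rate, all leave), 11% (20%, half leave) and 22% (20%, all leave). Restricting the set to subjects whose visit 7 was due returns 0.9%, 7.5% and 13%, matching the table.

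**The case against.** Five arguments weigh against the point.

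- **The phrase may be read more widely.** *Those subjects* could mean all subjects randomized to OPK-88003, with visit 7 only setting the timing. Section 8.1 leaves DSMB activities to a charter that is not among the documents. This is a possible reading, but the completer reading is the more natural one, and nothing in the documents settles it the other way.
- **Withdrawal is not automatic.** It needs a relatedness judgement, medical monitor consultation and a decision, and 5.1.1 favours retention. After week 8 a subject can miss doses, attend visit 7 and be counted. This limits how many are lost; those withdrawn are still uncounted.
- **The DSMB is not blind to leavers.** It assesses the safety of the dose, monitors at regular intervals and may recommend changes (8.1), and SAEs are reported within 24 hours (8.9.1.1). A reader might infer that an intolerable dose would go unseen. The documents do not support that; only the fixed trigger is affected.
- **High rates look unlikely.** Section 1.4.1 reports no severe or serious AEs in XNAB at about three times the modelled exposure (Cmax 11700/3755 = 3.1; AUC 1789/560 = 3.2), although nausea and vomiting there were frequent. At rates of 10% or less the wording hardly matters. This stands and is the main reason the point is minor.
- **The review may be past.** SAP 6.1 speaks of enrolment in the past tense. If so, only a re-count is left.

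SAP 8.2 reports more early discontinuations than expected. A reader might infer that subjects with GI events at 70 mg were missed. SAP 8.2 gives neither reasons nor arm, so that inference fails.

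**Conclusion.** The point holds in a narrow form and is minor: a change to consider. It does not question the trigger of five, the event definition or the choice of 70 mg, and it does not show that any decision was wrong. It rests on the literal reading of 8.10.2 and on some affected subjects being withdrawn within the two weeks before visit 7. The size depends entirely on assumed event rates and leaving shares: negligible at 10% or below, and material only from about 20 to 30% upward with substantial leaving.

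**What to change.** In 8.10.2, keep the timing, the event and the trigger of five. Replace *those subjects* with: all subjects randomized to OPK-88003 who received at least one 70 mg dose and whose visit 7 was due (first 70 mg dose at least 2 weeks earlier) by the review cut-off, whether or not they remained in the study. Align the DSMB charter, and state there that a subject who completed visit 7 early within the ±2-day window is included. Do not add subjects who stopped before their visit 7 was due unless their event-free contemporaries are added too.

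If the review has been held, re-count once on this set and report in the CSR whether the decision would have changed. The dosing, disposition and SAE data are already collected, and SAP 6.8 and 6.11.1 already tabulate injections and list SAEs and AEs leading to discontinuation, so no new SAP table is needed.

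The cost is one sentence, or one re-count. The downside is a somewhat more frequent cut to 60 mg because more than 10 subjects face the same trigger. At a 20% rate with half of affected subjects leaving, the chance is 7.5%, against 3.3% if nobody leaves.
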